**Multicenter double-blind placebo-controlled randomized
clinical trial of efficacy and safety of Tenoten for children in
the treatment of specific developmental disorders of
scholastic skills in children**

Phase III

Sponsor	ООО «NPF «MATERIA MEDICA HOLDING»
Protocol number	MMH-TD-005
Version date:	January 22, 2015
ClinicalTrials.gov Id:	NCT03159104

Protocol Summary

This document represents the protocol summary for the study on human subjects. The study will be carried out in accordance with ICH GCP, National Standard of the Russian Federation GOST 52379-2005 "Good Clinical Practice", Helsinki Declaration of World Medical Association, relevant requirements of the regulatory authorities as well as the study procedures.

Title of Study

Multicenter double-blind placebo-controlled randomized clinical trial of efficacy and safety of Tenoten for children in the treatment of specific developmental disorders of scholastic skills in children.

Phase: III

Sponsor: OOO «NPF «MATERIA MEDICA HOLDING», Moscow, Russia

Protocol No. MMH-TN-005

Objective of the study

- To evaluate efficacy and safety of Tenoten for children in the treatment of specific developmental disorders of scholastic skills in children.

Endpoints

Primary endpoint

1. Mean total scholastic skill score (reading, spelling and counting) in the groups after 12-week therapy compared to baseline.

Secondary endpoints

1. Mean score of "Reading skill test" in the groups after 12-week therapy compared to baseline.
2. Mean score of "Spelling skill test" in the groups after 12-week therapy compared to baseline.
3. Mean score of subtest No. 3 "Arithmetic" (of Wechsler Intelligence Scale for Children, WISC) in the groups after 12-week therapy compared to baseline.
4. Percentage of children with an increase in total scholastic skill score¹ (reading, spelling and counting) in the groups after 12-week therapy compared to baseline.
5. Efficacy Index according to Clinical Global Impression scaly by the end of therapy (CGI-EI).

¹ Improvement criterion – increased total scholastic skill score (reading, spelling and counting) by at least 5 points compared to baseline.

Safety assessment

- Occurrence and nature of adverse events (AE) during the treatment; AE severity, causal relationship to the study drug, and outcome.

Study design

A multicenter, double-blind, randomized, placebo-controlled clinical trial to evaluate the efficacy and safety of the study treatment.

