The study will enroll the school children (boys and girls) of grades 1, 2 and 3 of a regular school aged 7-9 years old (grade 1 school children will be enrolled at the beginning of the second half of the year) complaining of difficult learning classified according to ICD-10 as specific developmental disorders of scholastic skills (F81) including:

- specific reading disorder (F81.0);
- specific spelling disorder (F81.1);
- specific disorder of arithmetical skills (F81.2);
- mixed disorder of scholastic skills (F81.3);
- disorder simultaneously meeting criteria of F81.2+F81.0 or F81.2+F81.1, or F81.2+F81.0+F81.1.

The developmental disorders of scholastic skills will be verified by a doctor (either a neurologist or psychiatrist) according to reading, spelling, and counting tests. The children may have any concomitant diseases not considered as exclusion criteria and not requiring therapy during the following 12 weeks using the products specified in section "Forbidden concomitant therapy". Specific additional educational programs should not be performed within 12 weeks after enrollment either.

On signing information sheet (informed consent form) by the parent/adopter the patients will be examined by a neurologist or psychiatrist and tested for reading skills (method by L.A. Fotekova, T.V. Akhutina, 2002;), spelling skills (method by L.A. Fotekova, T.V. Akhutina, 2002) and counting skills (subtest No. 3 "Arithmetic" WISC test), and concomitant therapy will be recorded. If inclusion criteria are met and non-inclusion criteria are absent at Visit 1, the patient will be enrolled in the trial and randomized into one of the two groups: 1 tablet of Tenoten for children three times daily for 3 months (group 1) or the same dosing regimen of Placebo (group 2).

At Visit 1 the parents/adopters will receive the study product for 12-week treatment period and a diary to report any potential adverse events and cases of concomitant therapy.

Six weeks later (Week 6±3 days) a "Phone visit" (Visit 2) will be made in order to interview parents about the patient's condition, the presence / absence of concomitant diseases, adverse

events.

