At Visit 3 (Week 12±3 days) repeated testing of reading, spelling and counting skills will be made, complaints, data on concomitant diseases, concomitant therapy, and adverse events will be collected. The investigator will evaluate the subject's compliance and fill in the Clinical Global Impression Scale to calculate Efficacy Index (CGI-EI).

The patients will be allowed to take symptomatic therapy and medications for their co-morbidities during the study, except for the medicines listed in "Forbidden concomitant therapy".

Inclusion and exclusion criteria

Inclusion criteria

1. Children of either gender aged 7 to 9 years old.
2. School children of grades 1-3 (grade 1 children will be enrolled at the beginning of the second half of the year) in regular schools with state accreditation with principal educational program of elementary general education in compliance with Federal State Educational Standard of the Russian Federation.
3. Beginning of the second half of the year (only for 1st grades).
4. Specific developmental disorder of scholastic skills such as:
 - specific reading disorder (F81.0);
 - specific spelling disorder (F81.1);
 - specific disorder of arithmetical skills (F81.2);
 - mixed disorder of scholastic skills (F81.3; i.e. meeting the criteria for one of the following combinations: F81.2+F81.0, F81.2+F81.1, or F81.2+F81.0+F81.1).
5. Reading score of 15 to 35 on the Reading Skills test (L.A. Fotekova, T.V. Akhutina, 2002).
6. Spelling score of 15 to 30 on the Spelling Skills test (L.A. Fotekova, T.V. Akhutina, 2002).
7. Counting score of 5 to 15 on the subtest No. 3 "Arithmetic" (of Wechsler Intelligence Scale for Children).
8. Availability of a patient information sheet (Informed Consent Form) signed by the parent/adopter to confirm the child's participation in the clinical trial.

Exclusion criteria

1. History of the diseases:
 - Diseases of the nervous system, including:
 - inflammatory diseases of the central nervous system,
 - systemic atrophies,
 - extrapyramidal and movement disorders,
 - degenerative diseases of the nervous system,

- demyelinating diseases of the central nervous system,
- episodic and paroxysmal disorders,
- polyneuropathies,
- diseases of myoneural junction and muscle,
- cerebral palsy.
- Congenital malformations of the nervous system (excl. Spina bifida without hydrocephalus).
- Diseases and congenital malformations of eye causing impairment of vision.

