Storage conditions: Store below 25°C. Keep out of the reach of children.

Treatment duration

Tenoten/Placebo treatment duration is 12 weeks.

Observation period

In total the patients will be monitored for 12 weeks.

Symptomatic (Standard) treatment

[figure not shown]
Medicinal products and procedures required for the subjects including for the treatment of underlying and concomitant diseases except for the product included into section “Forbidden concomitant therapy”.

Prohibited concomitant therapy

Within 4 weeks prior to enrollment and throughout the study the subjects are not allowed to use any of the following medications (ATC group is specified in brackets):

1. Psycholeptic drugs (ATC group - N05) including anxiolytics (tranquilizers), hypnotics and sedatives.
2. Psychoanaleptics (ATC group – N06) including psychostimulants and nootropic drugs including:
 - pyrrolidine derivatives (racemates) – piracetam, etiracetam, aniracetam, etc.;
 - pyridoxine derivatives – pyritinol, biotredin;
 - GABA derivatives and analogues – gamma-aminobutyric acid, nicotinoyl gamma-aminobutyric acid, gamma-amino-beta-phenylbutyric acid hydrochloride, hopantenic acid, calcium gamma-hydroxybutyrate;
 - Ginkgo biloba;
 - neuropeptides and their analogues – methionyl-glutamyl-hidtidyl-phenylalanyl-prolyl-glycyl-proline;
 - amino acids and substances affecting excitatory amino acid system – glycine, pyridoxine+threonine;
 - Polypeptides and organic composites - bovine cerebral cortical polypeptides, cerebrolysin;
 - substances from other pharmacological groups with nootropic effect (general tonic drugs and adaptogens – acetylaminosuccinic acid, melatonin, lecithin, etc.).
3. Antiepileptic drugs (ATC group – N03A).
4. Anticholinergic drugs (ATC group – N04A).
5. Dopaminergic drugs (ATC group – N04B).
6. Antihypoxic and antioxidant drugs (ethylmethylhydroxypyridine succinate, citicoline, etc.).
7. Agents improving metabolism and energy supply to tissues, reducing tissue hypoxia (cytoflavin, corylip, eltacin, inosie, etc.).
8. Homeopathic remedies.
9. Drugs known to have caused allergic reactions.
10. Specific additional educational programs (forbidden during the study).

Study design scheme

Schedule of study procedures

Procedure	Visit 1 (Screening, Day 1)	Visit 2 Phone visit (Week 6 ±3 days)	Visit 3 (Week 12 ±3 days)
Informed consent	+		
Collection of complaints	+	+	+
Medical history	+		
Physical examination	+		+
Concomitant therapy	+	+	+

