Examination of reading skills (method by L.A. Fotekova, T.V. Akhutina, 2002)	+		+
Examination of spelling skills (method by L.A. Fotekova, T.V. Akhutina, 2002)	+		+
Examination of counting skills ("Arithmetic" subtest No. 3 of WISC)	+		+
Inclusion/exclusion criteria	+		
Randomization and prescription of study therapy	+		
Study drug supply	+		
Study drug accountability, compliance assessment			+
Distribution of diaries	+		
Evaluation of correct diary filling			+
Diary return			+
CGI-EI scale filling			+
Evaluation of treatment safety	+	+	+

Statistical Analyses

Samples

Total set includes all the subjects who have signed ICF. This sample will consider all adverse events throughout the study, including those occurred prior to the study therapy.

The sample including all subjects who received at least one dose of the study product to be used for ***analysis of the study treatment safety and tolerability*** (*Safety population*), as all adverse events identified after the study product administration will be recorded.

Full Analysis Set This sample will consist of all enrolled subjects, except for those who met at least one of the following criteria:

- 1) failure to meet inclusion/non-inclusion criteria;
- 2) subject failing to take any dose of the study drug;
- 3) absence of any data on the subject after randomization.

This was the best set for the Intention-to-treat method, so it will be used in the ***Intention-to-treat efficacy analysis of the test therapy***.

Per Protocol set. This sample includes all subjects who completed the therapy as per the study protocol, without any missing visits or major protocol deviations. This set will be used in the ***Per Protocol efficacy analysis of the test therapy***.

Mean value of the total set for the relevant day will be used to fill lacking/missing data.

Data treatment and all statistical calculations under the protocol will be made using SAS-9.3 statistical software.³

Evaluation of sample size

The sample size was assessed in accordance with the following rules and assumptions:

1. Statistical assumptions:

- 1.1 the power of statistical tests is 80% (the probability of correct rejection of the null hypothesis is 0.8)
- 1.2 the probability of type 1 error ' α ' is less than 0.05 (the probability of false acceptance of the alternative hypothesis)
- 1.3 statistical criteria used are two-sided

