- 1.4 value of clinically relevant " δ " difference is taken as equal to 5 (i.e. Tenoten for children effect is supposed to be clinically relevant compared to placebo effect if the effect in the study group exceeds the one in control group by at least 5 points)
- 1.5 statistical null and alternative hypotheses will be as follows:

³ Holder of license: OOO "NPF "MATERIA MEDICA HOLDING", No. 70100045.

$$H_0: m_1 - m_2 \leq \delta$$

$$H_1: m_1 - m_2 > \delta,$$

where m_1 - mean total scholastic skill score in Tenoten for children group

m_2 – mean total scholastic skill score in placebo group

δ – clinically relevant difference value.

1.6 an interim analysis is planned for potential adjustment of sample size:

- a. calculations will be made using O'Brien-Fleming boundary;
- b. proportions of the subjects completing the study and yielding the results for interim and final analyses, will be taken as 0.5 and 1.0 (i.e. interim analysis will be made after recruitment of half of the planned number of the clinical study subjects).

1.7 therefore, sample size will be calculated taking into account:

- a. interim analysis;
- b. assumption on expected effects declared in the main efficacy criterion of the protocol.

1.8 calculation of sample size in groups 1 and 2 for two-sided test for interim and final analysis will be made using the formula defining sample size (i.e. for the variant without interim analysis):

$$N_1 = N_2 = (\sigma_1^2 + \sigma_2^2) I,$$

where N_1 and N_2 are sample sizes in Tenoten for children and placebo groups

σ_1 and σ_2 – expected standard deviations in these groups

I – Fisher information determined using the formula:

$$I = (F^{-1}(1-\alpha) + F^{-1}(1-\beta))^2 / \theta_1^2,$$

where $F^{-1}(1-\alpha)$ and $F^{-1}(1-\beta)$ are tabular z-test values for α and β , a $\theta_1 = (m_1 - m_2)$.

1.9 final sample size will be determined using the formula:

$$N_F = N_{PP} / (1 - C_w),$$

where N_F – final sample size;

N_{PP} – result of calculation in cl. 1.8, i.e. scheduled number of subjects

completing the study per protocol;

C_w – withdrawal coefficient.

2. Assumptions on expected clinical study effects:

The difference between Tenoten for children effect consisting in increased mean total scholastic skill score by the end of therapy and effect in placebo group is supposed to be at least 10 points with standard deviation of at least 12 points.

Given the statistical terms and assumptions above each group size will be:

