- a) at interim analysis - 46 subjects
- b) at final analysis - 92 subjects.

Therefore, total PP set will include 184 subjects.

Taking into account that potential withdrawal of 30% subjects at the screening and during the study for various reasons, at least **132** subjects in each group will be required to sign informed consent (in total **264** subjects).

Statistical criteria

All statistical calculations will be made using two groups of statistical criteria:

- parametric - to evaluate continuous and interval random values;
- nonparametric – to obtain:
 - evaluations of equality/inequality of proportions of the subjects upon their comparison for various visits,
 - analysis of frequencies of the features compared,and
 - evaluation of continuous and interval random values in case of non-compliance with normal random distribution.

The following SAS procedures are suggested for interim analysis:

- SEQDESIGN, SEQTEST – design and performance of interim analysis;
- The terms of early termination of the study will be set using O'Brien-Fleming stopping boundary.

Parametric criteria

Prior to analysis using parametric statistics, data samples under comparison will be tested for normality (the Kolmogorov-Smirnov test).

The following parameters and approaches are to be used:

1. To evaluate the differences in continuous variables from two different (independent) groups – Student's test for independent samples.
2. To evaluate differences in continuous variables in one group at two different visits - Student's test for paired samples.
3. To evaluate time changes in parameters compared - analysis of variance (ANOVA) or modified repeated measures covariance (ANCOVA).
4. In case of multiple comparisons of the groups various corrections for multiplicity will be used, e.g. Dunnett, Tukey, Scheffe, Holm adapted test, etc.
5. Generalized Linear Models will be used in case of abnormal data distribution.

6. Selection of the type of distribution, specification of factor and covariance structures of the model will be made using fit-statistics such as AIC (Akaike information criterion).

The following SAS software programs are supposed to be applied to the above listed tests and techniques:

- UNIVARIATE: normality verification of the distributions under comparison;
- CORR, MEANS - calculation of descriptive statistics
- TTEST – Student's test with all modifications
- GLM – generalized linear models for analysis of time changes (ANOVA, ANCOVA)

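### The Per Protocol set excludes a child for any missing visit, so a missed Week-6 phone call alone removes complete primary outcomes from the set behind the 92 per group

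*Combined protocol and SAP*

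**What the plan says.** **Analysis set** (Statistical Analyses, Samples). The Per Protocol set is defined as follows: "This sample includes all subjects who completed the therapy as per the study protocol, without any missing visits or major protocol deviations". The word major qualifies deviations, not visits, and no visit is exempted. The same section defines a Full Analysis Set for the intention-to-treat efficacy analysis. Its three exclusion criteria are an eligibility failure, no dose taken, and no data at all after randomisation. A missed visit is not among them.

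**Visits** (Study design; Schedule of study procedures). There are three numbered visits. The second is headed "Visit 2 Phone visit (Week 6 ±3 days" and closes the bracket there. The call "will be made in order to interview parents about" the child's condition, concomitant diseases and adverse events. The schedule marks Visit 2 for complaints, concomitant therapy and safety only. At Visit 3, "repeated testing of reading, spelling and counting skills will be made". CGI-EI, drug accountability and compliance are marked at Visit 3 only.

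**Primary endpoint** (Endpoints): "Mean total scholastic skill score (reading, spelling and counting) in the groups after 12-week therapy compared to baseline".

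**Sample size** (Evaluation of sample size). The quantity N_PP is the "result of calculation in cl. 1.8, i.e. scheduled number of subjects" who complete the study per protocol. The conclusion reads: "Therefore, total PP set will include 184 subjects". This is raised to 264 to allow for 30% loss at screening and during the study, not broken down by reason.

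**The concern.** A Per Protocol set should hold the children who were treated as planned and whose outcome was measured as planned. A missed phone call at Week 6 alters neither. It takes away no term of the primary endpoint and no compliance record, yet the definition treats it like a missed Week-12 test.

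Two things are at stake. First, observed Week-12 scores from compliant children would be set aside in the analysis to which the sample size refers. Second, membership of the set would depend, after randomisation, partly on whether a parent could be reached by phone. A rule left this broad also invites case-by-case decisions later about which children count as per protocol.

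**Working it through.** **1. What each visit contributes** (Schedule of study procedures)

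| Item | Visit 1 | Visit 2 (phone) | Visit 3 |
|---|---|---|---|
| Reading, spelling, counting tests | yes | no | yes |
| CGI-EI | no | no | yes |
| Accountability and compliance | no | no | yes |
| Complaints, concomitant therapy, safety | yes | yes | yes |

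The primary endpoint uses Visits 1 and 3 only. Parents also record concomitant therapy and adverse events in the diary, which is returned at Visit 3.

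**2. Reproducing the plan's figure**

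Inputs, all from Evaluation of sample size: expected difference 10, margin 5, SD 12, two-sided alpha 0.05, power 80%, O'Brien-Fleming boundary with looks at 0.5 and 1.0, withdrawal 30%.

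- Fixed design: n = 2 × 12² × (1.960 + 0.842)² / (10 − 5)² = 90.42 per group.
- Two-look O'Brien-Fleming inflation, computed numerically: 1.0078. Then 90.42 × 1.0078 = 91.12, rounded up to 92 per group, 184 in total.
- Withdrawal: 92 / (1 − 0.30) = 131.4, rounded up to 132 per group, 264 in total.

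All three figures agree with the plan. So 92 is the number left **after** per-protocol exclusions, and the plan allows 264 − 184 = 80 children for losses of every kind.

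**3. If missed calls are already inside the 30%**

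The 264 stands. Let m be the share of otherwise per-protocol children who miss only the call. To end with 184, the other losses may be at most 264 − 184/(1 − m):

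- m = 5%: 264 − 193.7 = 70.3 children (26.6% of 264)
- m = 10%: 264 − 204.4 = 59.6 children (22.6% of 264)

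Power is unaffected within those limits, but part of the allowance is spent on children with complete outcomes.

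**4. If missed calls come on top of the 30%**

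The Per Protocol size per group is 92 × (1 − m), and the drift is 5 / (12 × √(2/n)). Power is the probability of crossing ±1.977 × √2 at the interim look or ±1.977 at the final look. The rates m are assumptions, because the documents give none.

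| m | n per group | Fewer children than 184 | Power | Total consenting to keep 92 per group |
|---|---|---|---|---|
| 0 | 92 | 0 | 80.4% | 264 |
| 2% | 90.2 | about 4 | 79.6% | 270 |
| 5% | 87.4 | about 9 | 78.3% | 278 |
| 10% | 82.8 | about 18 | 76.1% | 294 |
| 20% | 73.6 | about 37 | 71.1% | 330 |

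The last column is 2 × 92 / (0.70 × (1 − m)), rounded up within each group. The fixed-design formula Φ(drift − 1.96) gives nearly the same: 80.7% at 92, 78.5% at 87 and 76.6% at 83 per group.

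**The case against.** The strongest reply is that a strict set is coherent. Visit 2 is the only scheduled contact between Day 1 and Week 12. It asks about concomitant therapy, which bears on adherence because certain therapies are prohibited. Visit 3 information is retrospective, and the diary is described as covering adverse events and concomitant therapy, not complaints. This stands in part: without the call, there is no mid-treatment record of complaints. It does not rescue the rule, because the adherence-relevant items are collected twice elsewhere and compliance is judged at Visit 3 in any case.

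Three further objections stand and limit the point:

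- The Full Analysis Set keeps these children, with an observed Week-12 score that needs no imputation. The documents do not say which of the two efficacy analyses is primary.
- The 30% allowance is unspecified and may already include missed calls. A reader might infer that 9 to 18 of the planned 184 would be thrown away. On the plan's own definition, a child with a missing visit was never among the 184.
- The rule speaks of missing visits. It does not say that a late or repeated call counts as missing, so only a call that is never made is clearly caught.

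The planned interim analysis for possible sample-size adjustment might offset a shortfall, but its method is not detailed enough to rely on.

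**Conclusion.** The point holds as a defect of definition with a modest, conditional effect. The rule as written removes compliant children with complete primary outcomes from the Per Protocol analysis for an event that affects neither treatment nor measurement. There is no arithmetic error: 92, 132 and 264 all reproduce.

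The size depends on two things that the documents do not give: the missed-call rate, and whether the 30% covers it. If it does, power is unchanged. If it does not, power in the Per Protocol set falls from about 80% to about 78% at an assumed 5% missed, or 76-77% at 10%. At 2% the loss is under one percentage point.

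A reader might go further and conclude that 264 is too few, or that the outcomes are lost to the trial. The documents support neither: the allowance may be sufficient, and the intention-to-treat analysis retains these children.

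**What to change.** In the definition of the Per Protocol set, replace the requirement of no missing visit with three conditions: skill tests done at Visit 1 and Visit 3, treatment completed as the protocol specifies, and no major deviation. Add that a missed Visit 2 call alone is a minor deviation and does not exclude a child. Record this before unblinding.

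The call itself stays in the schedule with its safety role, and the sample size does not change. The cost is one sentence. The small downside is that, for children whose call was missed, mid-treatment information comes only from the diary and Visit 3, both of which are already collected.

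### Missing Week-12 scores in the FAS are filled with one mean pooled over both arms, which under random loss shrinks the treatment difference in proportion to the fraction missing

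*Combined protocol and SAP*

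**What the plan says.** All of this is in the combined protocol and SAP, mostly under Statistical Analyses, Samples.

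- The missing-data rule is one sentence: "Mean value of the total set for the relevant day will be used to fill lacking/missing data". No other method and no missing-data sensitivity analysis is given.
- The set that supplies the mean is defined just above: "Total set includes all the subjects who have signed ICF". It is not split by arm.
- The FAS, used for the intention-to-treat efficacy analysis, leaves out a child for only three reasons: "failure to meet inclusion/non-inclusion criteria", "subject failing to take any dose of the study drug" or "absence of any data on the subject after randomization".
- The Per Protocol set takes children who completed therapy "without any missing visits or major protocol deviations".
- Week 6 is a telephone contact without testing. Only at Visit 3 is it said that "repeated testing of reading, spelling and counting skills will be made", and CGI-EI is completed only there (Schedule of study procedures).

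**The concern.** A child who is eligible, takes the drug, is reached by telephone at Week 6 and then misses Visit 3 has some data after randomisation, so none of the three exclusions applies. That child enters the intention-to-treat comparison with a Week-12 result that is the same number in either arm. Screening failures in the Total set have no Week-12 score, so the Week-12 mean is in effect the mean of the tested children of both arms.

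Three things are at stake:

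- Under random loss the estimated difference is pulled toward zero.
- Filled values count as observed data, so the reported SE is smaller than the tested children can support.
- Part of any drug effect leaks into the placebo arm through the pooled mean. This matters for the paired within-group tests listed under Parametric criteria.

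The plan does not say whether the FAS or the Per Protocol set is primary, so the two could disagree because of this rule alone.

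**Working it through.** **Inputs from the plan** (Evaluation of sample size): expected difference 10, SD 12, margin 5 (null hypothesis m1 − m2 ≤ 5), two-sided 5%, power 80%, 92 completers and 132 consents per group, 30% withdrawal including screening losses.

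**Assumptions:** missing fractions of 5/10/20%, random and equal by arm; 132 per arm in the FAS, an upper limit because 132 is the number signing consent. Baseline SD is either 7.8 (correlation with Week 12 of 0.325) or 12 (correlation 0.5); both give a change SD of 12. The 7.8 is √((20² + 15² + 10²)/12), treating the three eligibility ranges (for example "Reading score of 15 to 35 on the Reading Skills test") as independent and uniform.

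**The plan's own figure.** With an excess over the margin of 10 − 5 = 5: n = 2 × 12² × (1.96 + 0.84)² / 5² = 90.4. Two-look O'Brien-Fleming inflation of 1.0078 gives 91.1, so 92; and 92/0.7 gives 132. An effect of 10 tested against zero would need only 23. The size therefore matches a test against the margin, where the planned excess is only 5 points.

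**Shrinkage.** With common fill M and equal loss f:
[(1−f)m1 + fM] − [(1−f)m2 + fM] = (1−f)(m1 − m2).
With unequal random loss and observed fractions p1 and p2, the factor is their harmonic mean, 2·p1·p2/(p1 + p2). For 20% lost on Tenoten and 10% on placebo: 10 × 2 × 0.8 × 0.9/1.7 = 8.5.

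**Reported SE and power.** The variance per arm of the filled change is V = (1−f)·144 + f·s² + f(1−f)·5². Here s is the baseline SD if the Week-12 score is filled (the literal reading, since the rule refers to a day), and s = 0 if the change is filled. SE = √(2V/132); power ≈ Φ((10(1−f) − 5)/SE − 1.96).

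Example, f = 0.20 and s = 7.8: V = 115.2 + 12.2 + 4.0 = 131.4; SE = 1.41; power ≈ Φ(3/1.41 − 1.96) ≈ 0.57 (simulated 0.56). The observed children alone give SE = 12√(2/105.6) = 1.65.

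| Missing per arm | 5% | 10% | 20% |
|---|---|---|---|
| Expected estimate (truth 10) | 9.5 | 9.0 | 8.0 |
| Margin power, Week 12 filled, baseline SD 7.8 | 0.87 | 0.78 | 0.56 |
| Margin power, Week 12 filled, baseline SD 12 | 0.86 | 0.76 | 0.51 |
| Margin power, change filled | 0.88 | 0.81 | 0.61 |
| Margin power, observed scores | 0.91 | 0.89 | 0.85 |

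Powers are simulated. At 30%, the upper bound, the estimate is 7.0 and power about 0.25 to 0.35, against 0.81. With exactly 92 tested per arm (Week 12 filled, baseline SD 12), power is 0.73/0.64/0.46 against 0.80.

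**Between-arm error rate.** Under random loss and no true difference, rejection stays at 5%: the SE shrinks along with the estimate. At a true difference of 5, false superiority over the margin is 1.7/0.8/0.3% instead of 2.5% (Week 12 filled, baseline SD 12).

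**Within-arm paired test, placebo.** Take a true placebo change of zero, a Tenoten effect of 10, 20% missing and the change filled. The placebo mean is pulled to 0.2 × 5 = 1.0. The reported SE is √(119.2/132) = 0.95; the actual SD is √((144/132)(1 + 0.04/1.6)) = 1.06. Rejection is about 21% by this formula and 21.6% simulated, against a nominal 5%. With Week 12 filled (baseline SD 12) it is 17.2%.

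**Loss that depends on outcome.** Suppose 20% are lost per arm, the lowest changers on Tenoten and a random 20% on placebo, with a true difference of 10. The estimate is about 9.6 (Week 12 filled, baseline SD 12) or 11.3 (change filled). Observed scores give about 14.1.

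**The case against.** The strongest case on the other side has four parts.

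- **Direction.** A reader might infer that the rule always biases toward zero and is therefore safe. That needs random loss. Criteria for Withdrawal or Termination allow parents to withdraw a child because the treatment is not working, and the last calculation shows an estimate above the truth. In that setting, at a true difference of 5 with the change filled, the margin is falsely crossed in nearly half of trials. This objection stands, and the shrinkage claim is limited accordingly.
- **Practical harm.** Between arms, under random loss, there is no false-positive inflation, and power against zero exceeds 0.99 at a difference of 10. The visible loss is against the 5-point margin, and the plan's Student's test is listed without a null value. This is fair, but the margin is in the stated hypotheses and is what reproduces 92 per group.
- **Target of estimation.** If children who leave Tenoten did no better than placebo, the effect in all randomised children would itself be (1−f) × 10. The plan states no such target, and the pooled fill reaches that value partly by raising the placebo arm. An effect of that kind should be chosen openly.
- **Size.** Baseline SD, correlation and the FAS missing rate are not in the documents, and 132 per arm ignores screening loss. This stands; hence the ranges.

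The paired-test figures need 20% loss, a 10-point drug effect and no placebo change over 12 weeks of schooling, so they illustrate rather than predict.

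**Conclusion.** The concern holds in a limited form. The rule pools both arms, reaches the intention-to-treat analysis, and is not repaired elsewhere in the document. Under random loss the FAS difference is (1−f) times the truth (the harmonic-mean factor if loss is unequal), and the SE is smaller than the observed data justify. That costs margin power: slight at 5% missing, marked at 20%. Paired within-arm tests reject too often.

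A reader might go further and infer that the rule inflates between-arm false positives, that the Per Protocol result is compromised, or that 30% of the FAS will be missing. The documents support none of these. Random loss leaves the between-arm test at its nominal level or below, the Per Protocol set admits no missed visit, and the 30% includes screening losses, so it is only an upper bound. When loss depends on outcome, neither the sign nor the size of the error can be fixed from the plan. This should be corrected before analysis; it does not invalidate the design.

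**What to change.** Delete the pooled-mean sentence. For the FAS:

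1. Use multiple imputation within each randomised arm (for example 20 imputations) of the Week-12 reading, spelling and arithmetic scores, from their baseline values, school grade and any Week-12 component observed.
2. Derive the total and responder status from the imputed components.
3. Compare arms on the total and the component scores by ANCOVA adjusted for baseline, combined by Rubin's rules. This is a new specification: Parametric criteria list ANCOVA only for changes over time.
4. Pre-specify a sensitivity analysis with placebo-based imputation for Tenoten withdrawals. Within-arm imputation also assumes loss is random given arm and the imputation variables, and it can overstate the effect if those who leave Tenoten are poor responders.

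An observed-score analysis removes the same bias under random loss and is an acceptable simpler choice, including for CGI-EI, which has no baseline.

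In simulation under random loss (grade not modelled), within-arm imputation with ANCOVA gave estimates of 9.9 to 10.1. Margin power at 5/10/20% missing ran from 0.90/0.88/0.84 (baseline does not predict change) to 0.95/0.95/0.94 (SD 12, correlation 0.5). Any gain over observed scores comes from baseline adjustment, not from imputation.

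The cost is SAP wording and modest programming. At 20% missing the SE is 1.46 instead of 1.50 (baseline SD 12), 1.59 instead of 1.41 (SD 7.8), or 1.68 instead of 1.41 if baseline does not predict change (1.68/1.41 = 1.19). It is thus slightly narrower to about 19% wider than under the Week-12 fill, and it reflects the data actually observed.
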